Patients must be able to read and comprehend English, except French patients from CCTG institutions. (See [§ 3.2.22](#))

Schema

* Regional Nodes will include axilla (Levels I, II, III), supraclavicular fossa and internal mammary nodes. If an axillary dissection has been performed, RT will only be directed to the un-dissected axilla.

** Patients will be stratified before randomization for immediate versus delayed and autologous versus implant only reconstruction. All reconstruction must be completed before radiation to be classified as immediate and autologous reconstruction is autologous tissue +/- implant.

All patients will undergo reconstruction of the breast; either before or after radiation, but it must be completed within 18 months after finishing radiation therapy, unless medically contraindicated.

Patients will be followed until 15 years after completion of radiation therapy or until death, whichever comes first ([§11.3](#))

Please refer to the full protocol text for a complete description of the eligibility criteria and treatment plan.

There is no surgical credentialing required for participation on this study.

Radiation therapy requires credentialing and submission of patient plans for review. See Sections [7.5](#) and [14.0](#) for more detail.

Table of Contents

Section	Page
1.0 BACKGROUND	8
1.1 Rationale for the Study	8
1.2 Baseline Toxicity from PMRT.....	9
1.3 Altered Fractionation in Breast Cancer.....	11
1.4 Patient Satisfaction and Well-being as Patient Reported Outcomes (PROs).....	12
1.5 Photographic Cosmetic Assessment	14
1.6 Study Hypotheses	14
2.0 OBJECTIVES	14
2.1 Primary Objective	14
2.2 Secondary Objectives.....	14
2.3 Photographic Cosmetic Assessment	15
2.4 Lymphedema Assessment.....	15
2.5 Patient Reported Outcomes (PRO) Objectives	15
2.6 Economic Analysis	15
2.7 Correlative Science Objectives	15
3.0 PATIENT SELECTION.....	16
3.1 On-Study Guidelines.....	16
3.2 Eligibility Criteria	17
4.0 PATIENT REGISTRATION.....	19
4.1 Investigator and Research Associate registration with CTEP.....	19
4.2 CTSU Site Registration Procedures	20
4.3 Patient Registration Requirements.....	22
4.4 Patient Registration/Randomization Procedures.....	22
4.5 Registration to Correlative and Companion Studies.....	23
4.6 Stratification Factors and Treatment Assignments	23
5.0 STUDY CALENDAR.....	25
6.0 DATA AND SPECIMEN SUBMISSION.....	26
6.1 Data Collection and Submission	26
6.2 Specimen collection and submission	28

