11.2 Criteria for discontinuation of protocol treatment

Radiation treatment will continue unless one of the following criteria applies:

- Disease progression or relapse
- General or specific changes in the patient's condition render the patient unacceptable for further treatment in the judgment of the treating physician
- Patient withdrawal or non-compliance
- Patient receives alternative treatment (non protocol treatment that replaces standard RT or RT not per protocol) before or during protocol treatment period
- Patient experiences reconstruction related complications to the ipsilateral breast prior to start of radiation. No further follow up will be required for these patients (see Section 11.4.2).

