11.3.2 Follow up for patients who do not complete radiation and breast reconstruction

Patients who complete radiation per protocol, but who do not complete reconstruction will also be followed as outlined in [Section 5.0](#) until disease recurrence, contralateral breast cancer, or a non-breast second primary cancer; or until an alternative treatment is given for up to 15 years

after the end of radiation therapy. All follow up (including survival) done after 5 years will be gathered by record review only.

Patients who experience disease recurrence, contralateral breast cancer, or a non-breast second primary cancer, or alternative treatment will discontinue protocol therapy and no further follow up will be required.

11.4 Managing Ineligible Patients and Registered Patients Who Never Receive Protocol Intervention

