11.4.1 Ineligible patients

Definition of ineligible patient: A study participant who is registered to the trial but does not meet all of the eligibility criteria is deemed to be ineligible.

Follow-up for ineligible patients who continue with protocol treatment: Patients who are deemed ineligible after registering may continue protocol treatment, provided the treating physician, study chair, and executive officer agree there are no safety concerns if the patient continues protocol treatment. All scans, tests, and data submission are to continue as if the patient were eligible. Notification of the local IRB may be necessary per local IRB policies.

Follow-up for ineligible patients who discontinue protocol treatment: For patients who are deemed ineligible after registering to the trial, who start treatment, but then discontinue study treatment, the same data submission requirements are to be followed as for those patients who are eligible and who discontinue study treatment.

11.4.2 Follow-up for patients who are registered, but who never start study treatment:

For all study participants who are registered to the trial but who never receive study intervention* (regardless of eligibility), the follow-up requirements are specified below.

- Baseline, off treatment, and end of study form required. See the Data Submission Schedule accompanying the All Forms Packet.
- * Patients who experience reconstruction related complications before the start of radiation will not receive protocol treatment, and the end of study form will be completed for these patients.

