12.2 Sample Size, Accrual Time and Study Duration

Our target sample size will be 792 evaluable patients (396 in each arm). To account for 10% drop-out due to cancellations or protocol deviations, our target accrual is 880 patients (440 per arm) (90% of 880 is 792).

The study design is a randomized, un-blinded, non-inferiority trial. It is assumed that the two-year breast reconstruction complication rate for the control arm (Arm 1: standard fractions) is 25%. Other assumptions for the sample size determination include:

- α (one-sided) = 0.025
- power = 90%
- non-inferiority margin: the absolute increase in the proportion of patients who experience
- a breast reconstruction complication within two-years is 10% above that of the control arm.
- one interim analysis (when 30% of the information is obtained) for futility

Under an alternative hypothesis that the true rates in the two arms are equal, a sample size of 792 (396 per arm) evaluable patients would give us 90% power to reject the null hypothesis of inferiority. The final analysis will take place after all patients have reached two years post-radiation. The anticipated accrual period is approximately 30 months, and the total study duration is approximately 60 months. We anticipate being able to accrue approximately 30 patients per month based on our best estimate extrapolated from recently closed intact breast trials looking at similar fractionations. It should be noted that if we instead assumed a complication rate of 50% in the control arm (the most statistically conservative, in terms of sample size), the above sample size would still give us approximately 80% power to reject the null hypothesis of inferiority (again with one-sided α of 0.025).

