Simulation studies of 10,000 clinical trials are conducted for the proposed group sequential design. The probabilities of early stopping (at the interim analysis) and empirical powers for various scenarios are summarized in the following table. Of particular interest, assuming that the two-year breast reconstruction complication rate is 25% for the control arm (Arm 1: conventional PMRT) and 35% for the hypofractionated PMRT (Arm 2), where the Arm 2 treatment is inferior to Arm 1, there is a 14.45% chance of stopping the trial early to conclude that hypofractionated PMRT is inferior. In another scenario where the complication rate of the conventional PMRT is 25% and that of hypofractionated is 25%, where the Arm 2 treatment is truly non-inferior to Arm 1, the likelihood of stopping early to conclude inferiority is 0.24% and the likelihood of the trial concluding that hypofractionated PMRT is non-inferior to conventional one is 90.84% (power).

Reconstruction complication rate		Interim analysis conclusion		Early stopping	Final analysis conclusion		Rejection (of H_0) rate
Conventional	Hypofractionated	Noninferior	Inferior		Noninferior	Inferior	
25%	35%	0.00%	14.45%	14.45%	2.37%	83.18%	2.37%
	30%	0.00%	2.86%	2.86%	34.51%	62.63%	34.51%
	25%	0.00%	0.24%	0.24%	90.84%	8.92%	90.84%

It should be noted that the primary analyses will be an intent-to-treat analysis where all patients randomized will be included in the analysis and will be analyzed based on the arm they were randomized to regardless of actual radiation schedule received. This analysis will not be stratified. Due to the random treatment assignment with stratification for the timing of reconstruction and type of reconstruction, it is expected that the baseline patient characteristics, including the planned reconstruction procedures, are roughly balanced across the two treatment arms. A sensitivity analysis stratified by timing and type of reconstruction surgery will be conducted.

The frequency and the proportion of patients who enrolled in the trial prior to reconstruction surgery who did not receive the surgery within 18 months of radiation as specified in the eligibility criteria will be summarized separately by arm. A secondary analysis excluding these patients will be conducted.

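### The primary analysis is intent-to-treat on all randomised patients, but Section 11 ends required follow-up before 24 months for several groups and no rule says how they enter the test

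*Combined protocol and SAP*

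**What the plan says.** All references are to the combined protocol and SAP.

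**Analysis.** Section 12.3.2 says that "the primary analyses will be an intent-to-treat analysis where all patients randomized will be included in the analysis", each patient in the assigned arm whatever schedule was actually given. The test is an unpooled two-sample Z on raw proportions, with the number of patients per arm as denominators. The event window is two years from the end of radiation.

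**Follow-up.** Section 11 releases patients in three ways:
- Recurrence, contralateral cancer, a non-breast second primary or alternative treatment. Section 11.3.2 says such patients "or alternative treatment will discontinue protocol therapy and no further follow up will be required". Sections 11.3.1, 11.4.3 and 11.5 use the same stop events. Section 11.2 defines alternative treatment to include radiation not given per protocol.
- A reconstruction complication before radiation. Section 11.2 reads: "Patient experiences reconstruction related complications to the ipsilateral breast prior to start of radiation. No further follow up will be required for these patients".
- Never starting treatment. Section 11.4.2 reads: "Baseline, off treatment, and end of study form required".

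None of these rules has a 24-month floor. The schema says something different: "Patients will be followed until 15 years after completion of radiation therapy or until death, whichever comes first".

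**Sample size.** Section 12.2 plans 792 evaluable patients out of 880: "To account for 10% drop-out due to cancellations or protocol deviations". Section 12.5 repeats 792 as the number evaluable for the primary endpoint.

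**Missing data.** Section 12.6 is triggered when more than 5% of patient information is missing. It promises to add covariates to the primary analysis, but it defines the missingness mechanisms through patient-reported outcome scores.

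**The concern.** Followed as written, Section 11 leaves some randomised patients without a 24-month complication status, so the analysis stated in Section 12.3.2 cannot be carried out on everyone randomised. This is a conflict between stated rules, not just a missing detail. Patients who receive a different radiation schedule are the ones an as-randomised analysis is meant to retain, and alternative treatment is one of the events that ends follow-up.

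For patients who never receive radiation the problem goes further: a window that starts at the end of radiation has no start date. That group includes patients who had a reconstruction complication before radiation, and the plan does not say whether that complication counts.

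At stake is the non-inferiority conclusion. The Z test needs a yes or no for each patient in the denominator. If unobserved patients enter as complication-free in equal shares, both rates and their difference shrink towards zero, which favours a non-inferiority claim. If they are left out, the population is no longer the one declared. The choice would have to be made after the data exist, in an unblinded trial.

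**Working it through.** **Inputs from Section 12.2.** Control rate 25%; margin 10 points; "α (one-sided) = 0.025"; power 90%; 396 evaluable per arm; 440 accrued per arm.

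**Step 1. Reproduce the plan.** n per arm = (1.960 + 1.2816)² × 2 × 0.25 × 0.75 / 0.10² = 394.03, so 395 per arm or 790, against 792 stated. 792 / 0.90 = 880, exact. Power at 396 per arm: SE = √(0.375/396) = 0.03077; 0.10/0.03077 − 1.96 = 1.29; power 90.1%. At a 50% control rate the same formula gives 80.4%, against about 80% stated. Simulating the design with its futility look gives power 90.0% (stated 90.84%) and error 2.46% (stated 2.37%). The sample size is sound.

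**Step 2. Unobserved patients scored complication-free.** Assumptions: true rates 25% and 35% (exactly at the margin), 440 per arm, a share u unobserved in each arm with the same underlying rates as the rest and no events captured. Observed rates are q₁ = 0.25(1 − u₁) and q₂ = 0.35(1 − u₂). Error = P(N(0,1) > 1.96 − (q₁ − q₂ + 0.10)/SE), with SE = √[q₁(1 − q₁)/440 + q₂(1 − q₂)/440].

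Worked at 10%: q₁ = 0.225, q₂ = 0.315, SE = √(0.39015/440) = 0.02978; 0.010/0.02978 = 0.336; P(N(0,1) > 1.624) = 5.2%.

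| Unobserved, Arm 1 / Arm 2 | Observed difference | One-sided error |
|---|---|---|
| 0% / 0% | 10.0 points | 2.5% |
| 5% / 5% | 9.5 | 3.6% |
| 10% / 10% | 9.0 | 5.2% |
| 15% / 15% | 8.5 | 7.4% |
| 10% / 10%, half their events captured | 9.5 | 3.6% |
| 5% / 10% | 7.75 | 11.3% |
| 12% / 8% | 10.2 | 2.1% |

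These are fixed-sample figures. Simulating with the futility look barely changes them (5.21% at 10%/10%). Scoring the 10% as events instead gives rates of 32.5% and 41.5%, again 9 points apart, and 4.9% error, so reversing the imputed value is no cure.

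**Step 3. Unobserved patients dropped.** If loss is unrelated to outcome, error stays at 2.5% and power is 91.6%, 90.1% or 88.5% at 5%, 10% or 15% loss. If 10% are dropped per arm, and those dropped in Arm 2 have a true rate of 45% against 35% overall, the observed Arm 2 rate is (0.35 − 0.10 × 0.45)/0.90 = 33.9% and the error is 5.3%. At 50% it is 7.5%.

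**Step 4. Everyone followed.** 440 per arm: SE = √(0.375/440) = 0.02919; 0.10/0.02919 − 1.96 = 1.465; power 92.9%, error 2.5% (fixed-sample).

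**The case against.** The best defence is that the plan implies an evaluable-patient analysis and was sized for it. Sections 12.2 and 12.5 both speak of 792 evaluable patients, which points to leaving unobserved patients out, not to scoring them as non-events. With loss unrelated to outcome, that costs nothing beyond the power already allowed for. This stands as arithmetic. It does not rescue the plan, because Section 12.3.2 declares a different population and nothing makes the loss unrelated to outcome.

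Second, the error figures for scoring as complication-free sit at the upper end for equal loss unrelated to outcome. Section 5.0 records complications before radiation, at its completion, at 2 to 8 weeks and at 6, 12, 18 and 24 months, so a patient whose cancer recurs at month 18 already has most of the window observed. Nor is the direction guaranteed, as the 12%/8% row shows. Both points stand.

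Third, several off-plan groups remain under follow-up: patients given a scar boost (Section 7.4), ineligible patients who continue treatment (11.4.1), those irradiated but never reconstructed (11.3.2), and those who withdraw after starting, until a stop event (11.4.3). The 10% allowance is for cancellations and protocol deviations, not for loss of endpoint status. This also stands. It limits how many patients are affected but supplies no rule for the rest.

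Fourth, Section 12.6 is not confined to patient-reported outcomes: its trigger is general and it mentions the primary analysis. It still gives no usable rule for a binary complication status.

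**Conclusion.** The conflict is certain from the text; its size is not. Section 12.3.2 requires an outcome for everyone randomised, Section 11 stops collecting it for several groups, the schema contradicts Section 11, and no section says how a missing status or a death enters the test.

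Under an assumed 5% to 15% unobserved in each arm, scored complication-free with no events captured, the one-sided error is 3.6% to 7.4%. Partial capture lowers this, and unequal loss can move it either way (2.1% to 11.3% in the cases shown). Random dropping leaves it at 2.5%.

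Stronger readings go beyond the documents:
- A reader might infer that many patients are affected. No rate is given for recurrence, new cancer, alternative treatment or pre-radiation complications.
- A reader might infer that the plan scores these patients as complication-free. The plan is silent, and its evaluable count points the other way, so 5.2% is a scenario and not the trial's error rate.
- A reader might infer that an abandoned reconstruction is automatically a non-event. Failed reconstruction, implant removal and unplanned admission or surgery all count under Section 10.1, and Section 12.3.2 reports patients not reconstructed within 18 months by arm, with a secondary analysis excluding them.

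**What to change.** 1. In Sections 11.2 to 11.5, separate coming off protocol treatment from coming off study. Collect Section 10.1 complications and vital status to 24 months, by record review where visits have stopped, on every randomised patient who has not withdrawn consent, whatever happens after randomisation. Treatment rules are unaffected.
2. In Section 12.3.2, define the time origin for patients who never start radiation, and say whether a complication before radiation counts. State how deaths and residual missing status enter the test. One option is the 24-month cumulative incidence per arm with death as a competing event, a method Section 12.4.1 already uses for recurrence, with the difference tested against 0.10.
3. Add a tipping-point sensitivity analysis for patients still without status.
4. Reconcile the schema with Section 11, and the evaluable count in Sections 12.2 and 12.5 with the intent-to-treat statement.

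A per-protocol analysis, and a sensitivity analysis counting a reconstruction abandoned for medical reasons as an event, are optional.

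The cost is protocol wording plus chart review to 24 months for the patients now released. No extra patients are needed: following all 880 gives 92.9% power at 2.5% error. The change should not be expected to repair the recurrence or QALY analyses. It collects no recurrence data, and the EQ-5D-3L is completed by the patient and cannot be recovered from charts.

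### No analysis by radiation schedule received supports the single intent-to-treat non-inferiority test, and Sections 12.2 and 12.3.2 handle the expected 10% of cancellations or deviations differently

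*Combined protocol and SAP*

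**What the plan says.** Section 12.3.2 declares non-inferiority when one unpooled Z statistic exceeds 1.96. The analysis is intent-to-treat on all randomised patients, who "will be analyzed based on the arm they were randomized to regardless of actual radiation schedule received". Two further analyses of the primary endpoint are planned there. One is a sensitivity analysis stratified by timing and type of reconstruction. The other is a secondary analysis excluding patients enrolled before reconstruction who did not have it within 18 months of radiation. Neither has a part in the decision rule, and neither is defined by the radiation received. As a category, per protocol appears only in the radiotherapy quality grades of Sections 7.5.4 and 7.5.5, which are not linked to any outcome analysis.

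Section 12.2 sets the size: "Our target sample size will be 792 evaluable patients (396 in each arm"). The accrual figure follows: "To account for 10% drop-out due to cancellations or protocol deviations, our target accrual is 880 patients (440 per arm"). Section 12.5 repeats the step and describes the 792 as evaluable for the primary endpoint.

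On data collection, Section 11.4.2 asks only for baseline, off-treatment and end-of-study forms from patients who never start radiation. Section 11.2 counts radiotherapy not given per protocol as alternative treatment, and Section 11.3.2 requires no further follow-up after alternative treatment. Section 12.6 on missing data is framed around patient-reported outcomes and gives no counting rule for the primary endpoint.

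**The concern.** In a superiority trial, non-adherence usually works against the claim. In a non-inferiority trial it can work for it. A patient who receives the other arm's schedule, or who is never irradiated and enters the denominator as event-free, shrinks a true excess of complications and makes a difference at the margin easier to miss. The trial is also unblinded. With intent-to-treat as the only analysis by arm, nothing in the plan would show whether this had happened.

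Sections 12.2 and 12.3.2 also disagree about who is analysed. The first treats the cancelled and deviating 10% as outside the evaluable set; the second includes everyone randomised, with a target of 880. The intended denominator, and what is entered for patients with no 24-month result, are left open.

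**Working it through.** **Inputs (Section 12.2).** "α (one-sided) = 0.025"; power 90%; control rate 25%; margin an absolute 10 points; 396 evaluable per arm; 440 randomised per arm. Power is computed "Under an alternative hypothesis that the true rates in the two arms are equal". The test is the one in Section 12.3.2:

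Z = (p1 − p2 + 0.10) / √[p1(1−p1)/n + p2(1−p2)/n], non-inferior if Z > 1.96.

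**Reproducing the plan.**
- n per arm = (1.960 + 1.2816)² × 2 × 0.25 × 0.75 / 0.10² ≈ 394.03, rounded up to 395 (stated 396).
- 792 / 0.90 = 880, as stated.
- Power at 396 per arm: SE = √(0.375/396) = 0.03077; Φ(0.10/0.03077 − 1.96) = 90.1%. Simulated with the interim futility look (Z < −1.007) it is 90.0%, against 90.84% stated.
- At a 30% hypofractionated rate: 35.1% against 34.51% stated. At 35%: 2.5% against 2.37% stated.

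The design figures are sound for 396 per arm.

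**Effect of non-adherence on the intent-to-treat test.** True rates are 25% and 35%, exactly at the margin, with n = 440 per arm. A fraction f is affected. The value of f and the outcomes of these patients are assumptions, because the documents give neither. The chance of a false non-inferiority conclusion is Φ[(p1 − p2 + 0.10)/SE − 1.96].

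- One-way: fraction f of the hypofractionated arm gets the control schedule. p1 = 0.25, p2 = 0.35 − 0.10f.
- Untreated and counted event-free, both arms: p1 = 0.25(1−f), p2 = 0.35(1−f).
- Two-way: fraction f of each arm gets the other schedule. p1 = 0.25 + 0.10f, p2 = 0.35 − 0.10f.

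Example, two-way at f = 10%: p1 = 0.26, p2 = 0.34; SE = √[(0.1924 + 0.2244)/440] = 0.03078; Φ(0.02/0.03078 − 1.96) = Φ(−1.31) = 9.5%.

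| f | One-way | Untreated, event-free | Two-way |
|---|---|---|---|
| 0 | 2.5% | 2.5% | 2.5% |
| 2.5% | 3.0% | 3.0% | 3.6% |
| 5% | 3.6% | 3.6% | 5.1% |
| 10% | 5.1% | 5.2% | 9.5% |

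Simulation with the interim rule (400,000 trials per cell) agrees to within 0.1 percentage point.

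**A per-protocol set beside it.** If 396 per arm remain and exclusion is unrelated to outcome, the same test has a 2.5% false-positive rate at 25% v 35% and 90.1% power at equal rates.

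**The case against.** Intent-to-treat is the comparison that randomisation protects, and keeping it primary is defensible. That stands.

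The strongest objection is to the mechanism. A reader might infer that the whole expected 10% pulls the arms together. The documents do not support this:
- Section 12.2 names cancellations and deviations without splitting them and projects no crossover rate.
- Patients who never start radiation have no 24-month outcome, so they dilute only if counted as event-free, which the plan does not say.
- Many patients given another schedule would fall under alternative treatment, after which follow-up is not required.
- The deviations that Section 7.5 grades are dose-volume and contouring failures. These, and a scar boost (Section 7.4), can occur within the assigned schedule and need not move complication rates towards the other arm. A failure to prescribe the proper dose (Section 7.4) could include wrong-schedule cases, but no frequency is given.

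All of this stands. Much of the 10% is therefore a missing-outcome problem rather than a dilution problem. That leaves its own gap, since the primary endpoint has no rule for such patients.

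A second objection is that the planned exclusion of unreconstructed patients is already a partial per-protocol analysis. It is, but on surgery; it cannot show the effect of radiation non-adherence.

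A third is that a per-protocol set conditions on events after randomisation. One arm must complete 25 fractions and the other 16, so non-completion may differ by arm and be related to prognosis, and the bias can go either way. This also stands, and it limits the role such an analysis should have.

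**Conclusion.** The gap is real and inexpensive to close. The non-inferiority conclusion has no supporting analysis by radiation received, and Section 12.2's evaluable 792 does not match Section 12.3.2's all randomised.

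The size rests on assumptions about how many patients are affected and what is recorded for them: 3.0–3.6%, 3.6–5.1% and 5.1–9.5% false non-inferiority for 2.5%, 5% and 10% per arm (in the one-way case, of the hypofractionated arm only), against a nominal 2.5%. A reader might take 9.5% as the error rate to expect. It is a worst case: it needs the entire 10% in both arms to switch schedules fully and still contribute a 24-month outcome.

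Nor do the documents support the inference that the intent-to-treat test is invalid, or that non-inferiority should be claimed only if both analyses succeed. A supportive analysis is enough. Confidence is medium, because the direction and size of any effect depend on a split that the plan does not give.

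**What to change.** In Section 12.3.2:

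1. Add a pre-specified supportive per-protocol analysis of the primary endpoint, using the same Z statistic and 10-point margin, in eligible patients who received their assigned fractionation. Fix membership before outcomes are reviewed. Report it beside the intent-to-treat result, with reasons for exclusion by arm, and discuss any discordance. It accompanies intent-to-treat; it neither replaces it nor acts as a co-primary test.
2. State how randomised patients without a 24-month outcome are counted, including those who never start radiation and those whose follow-up ends after alternative treatment.
3. Reconcile Section 12.2 with Section 12.3.2: say whether the 792 evaluable patients are the set for the supportive analysis, an allowance for missing outcomes, or something else, and which denominator the primary test uses.

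The cost is wording and one more analysis. No extra patients are needed, since 396 per arm already gives about 90% power at equal rates. The downside is that the per-protocol result may be biased in either direction, so a discordant finding would have to be explained.

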Research has found that PMRT is an independent risk factor for complications in patients undergoing breast reconstruction. Radiation-associated complications include infection, seroma, delayed wound healing, capsular contracture, implant removal, fat necrosis and poor cosmetic results. A recently published claims-based review evaluated the complications for 14,894 reconstructed patients with an average age of 54. [29] They found a rate of 5-10% wound healing difficulty, 20% infection, 25% implant removal and 16% fat necrosis (autologous). These numbers included patients undergoing both implant and autologous reconstruction, with and without radiation therapy (RT), and RT was associated with an increased risk of infection, implant removal and fat necrosis. To ensure a sufficient event rate, we've selected a conservative composite reconstruction event rate of 25% in our standard treatment arm. Reflecting the heterogeneity of breast reconstruction practiced in the country, in this trial we plan to allow a variety of reconstruction techniques, given the controversy over superiority in the literature: immediate or delayed implants, autologous tissue, or a combination of both. We also plan to allow the use of acellular dermal matrix or similar soft tissue augmentation matrices.

Benediktsson et al. 2006[30]	107 pts. PMRT & Immediate reconstruction, saline prosthesis	41.7% Baker 3 or 4 contracture	
Christante, et al. 2010[31]	100 pts. PMRT & Immediate breast reconstruction	44% complications and 31% required implant removal	Delayed reconstruction patients had only a 22% complication rate
Cordeiro et al. 2004[32]	159 pts. Recon before RT	68% contracture with 80% patient good cosmesis	
Alderman, et al. 2002[33]	326 pts. PMRT, 12 centers	52% complications in immediate reconstruction	Delayed reconstruction rate 33%
Whitfield, et al. 2008[34]	42 pts. PMRT implants or TEs, 40Gy in 15 fractions	19.5% revisional surgery for capsular contracture	
Jhaveri, et al. 2008[35]	92 pts. PMRT and Immediate recon	25% rate of severe complications (Surgery or IV antibiotics)	0% complication autologous tissue recon
Fowble, et al. 2015[36]	99 pts. Immed TE and PMRT	18% failure rate 3.8 yrs.	

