4.6 Stratification Factors and Treatment Assignments

The factors listed below will be used as stratification factors. After a patient has been registered, the values of the stratification factors will be recorded, and the patient will be assigned to either hypofractionated or standard radiation dosing using the Pocock and Simon dynamic allocation

procedure, which balances the marginal distributions of the stratification factors between the treatment groups (Pocock-Simon).

Patients will be stratified before randomization based on planned intent for:

- autologous (+/- implant) vs.
- implant only breast reconstruction.
- Patients will be stratified before randomization based on:
 - immediate reconstruction vs.
 - planned for delayed breast reconstruction (**includes patients who have had no reconstruction or only a temporary expander placed at time of randomization.**)
- ** Patients undergoing immediate reconstruction will already have completed reconstruction at the time of randomization.
- *** Patients who have a tissue expander placed at the time of mastectomy and then have a delayed final reconstruction will be classified as delayed for purposes of stratification and randomization.

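### Allocation is balanced on planned reconstruction type and timing, but the primary non-inferiority test leaves both out; if they are prognostic, the test is mildly conservative and about 1 to 2 points of power go unused.

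*Combined protocol and SAP*

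**What the plan says.** Section 4.6 uses two stratification factors: planned type (autologous with or without implant, against implant only) and timing (immediate against planned delayed). Allocation is by the Pocock-Simon procedure, "which balances the marginal distributions of the stratification factors between the treatment groups". A patient with only a temporary expander at randomisation counts as delayed.

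The primary statistic in Section 12.3.2 is the difference in two-year complication proportions plus 0.1, divided by the unpooled binomial standard error of the two arms. The plan states openly that "This analysis will not be stratified". The reason given is that stratified randomisation should leave baseline characteristics roughly balanced. It adds: "A sensitivity analysis stratified by timing and type of reconstruction surgery will be conducted". It does not say which stratified estimator that will be, or whether type and timing are taken as planned or as received.

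Section 12.2 sizes the trial for a single rate per arm, with no stratum rates or shares.

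**The concern.** Expected balance answers a worry about bias. It does not make the crude standard error correct. When allocation forces the arms to have the same mix of low-risk and high-risk patients, that mix no longer contributes to the sampling variation of the treatment difference. The crude formula p(1−p)/n still includes it. The more successful the balancing and the more prognostic the factors, the more the crude standard error overstates the true one.

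The Section 1.2 table gives some reason to expect prognostic strata. Two series report 44% against 22% and 52% against 33% for immediate against delayed reconstruction. A third, with 25% severe complications overall, reports "0% complication autologous tissue recon".

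At stake is precision: the interval that decides non-inferiority would be somewhat wider than it needs to be, so a truly non-inferior schedule would fail slightly more often.

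**Working it through.** **Inputs from Section 12.2.** "α (one-sided) = 0.025"; control rate 25%; margin 0.10 absolute; equal true rates under the alternative; 396 evaluable per arm.

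**The plan's own figures.**
- n per arm = 2 × 0.25 × 0.75 × (1.960 + 1.2816)² / 0.10² = 394.03, so 395, against 396 stated.
- Crude SE = √(2 × 0.1875/396) = 0.03077. Power = Φ(0.10/0.03077 − 1.96) = Φ(1.290) = 90.1%.
- Simulating the design with its futility look (400,000 runs) gives power 90.0% against 90.84% stated, and rejection at 25% v 35% of 2.46% against 2.37%.

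The design reproduces with the unstratified test.

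**Formulas with prognostic, balanced strata** (share w, rate p, overall rate held at 25%, no interim look):
- Within-stratum variance V = Σ w·p(1−p), to set against the crude 0.1875; true SE = √(2V/396).
- Stratified power = Φ(0.10/SE_true − 1.96).
- Actual power of the crude test = Φ((0.10 − 1.96 × SE_crude)/SE_true). The crude test keeps its wide critical distance, but the estimate varies with the smaller SE.
- Actual error of the crude test at the margin = Φ(−1.96 × SE_crude/SE_true), both recomputed with Arm 2 ten points higher in every stratum.

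**Worked case: equal strata at 37.5% and 12.5%.**
- V = 0.5 × 0.2344 + 0.5 × 0.1094 = 0.1719, which is 8.3% below 0.1875. SE_true = 0.02946, which is 4.3% below 0.03077.
- Stratified power = Φ(1.434) = 92.4%.
- Crude power = Φ((0.10 − 0.06031)/0.02946) = Φ(1.347) = 91.1%.
- At the margin the two-arm variance sums are 0.4150 crude and 0.3837 within strata, so the SEs are 0.03237 and 0.03113. Error = Φ(−2.038) = 2.1%.

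**Other cases, by the same formulas.** Every stratum rate and share is an assumption.

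| Strata | V | SE smaller by | Stratified power | Crude power | Forgone (points) | Crude error |
|---|---|---|---|---|---|---|
| 38.3% / 19.3%, 30:70 (19-point gap) | 0.1799 | 2.0% | 91.3% | 90.6% | 0.7 | 2.3% |
| 30% / 10%, 75:25 | 0.1800 | 2.0% | 91.3% | 90.6% | 0.7 | 2.3% |
| 36% / 14%, 50:50 (22-point gap) | 0.1754 | 3.3% | 91.9% | 90.9% | 1.0 | 2.2% |
| 37.5% / 12.5%, 50:50 | 0.1719 | 4.3% | 92.4% | 91.1% | 1.3 | 2.1% |
| 40% / 10%, 50:50 | 0.1650 | 6.2% | 93.4% | 91.5% | 1.8 | 1.9% |
| Two factors, 22 points each (51.4 / 29.4 / 29.4 / 7.4%; shares 15, 15, 35, 35%) | 0.1652 | 6.1% | 93.3% | 91.5% | 1.8 | 1.9% |

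Simulation without the interim look agrees. For one factor with a 19 to 22 point gap and 30 to 50% of patients in the high-risk stratum, crude power is 90.6 to 90.8%, stratified power 91.4 to 91.9%, and crude error 2.2 to 2.3%. For two 22-point factors the figures are 91.5%, 93.5% and 1.9%.

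**The case against.** The strongest defence is that this is a disclosed, coherent and conservative choice. Sample size, test statistic and final boundary all use the same unstratified comparison. The reason is stated and the stratified result will be reported anyway. All of that stands, and it limits the severity. It does not show that the crude standard error is right.

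A second objection is that the prognostic strength is uncertain here, and this also stands. The 25- and 30-point gaps in the table exceed the 19 and 22 points cited for timing. The evidence on type comes from one series of 92 patients, all with immediate reconstruction, and on a narrower outcome (surgery or IV antibiotics) than the composite in Section 10.1. Expander patients count as delayed in this trial, so the cited timing gaps may shrink. Stratum shares are not given. Pocock-Simon balances margins and not the four cells, so realised gains may differ slightly.

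Three stronger readings are tempting, and the documents support none of them:
- A reader might infer that the trial is underpowered. The crude test reproduces the planned 90%, and its actual power is above that in every case tabulated.
- A reader might infer a loss of 2 to 3 points by comparing 92.4% or 93.4% with 90.1%. But 90.1% is the crude test's power when strata do not matter. Under the same strata it is 91.1% or 91.5%, so the loss is 1.3 or 1.8 points.
- A reader might infer that the test is invalid or could favour a false claim. The error runs the other way: the true one-sided rate falls below 2.5%.

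**Conclusion.** The point holds as a minor efficiency correction. If planned type and timing are prognostic to the degree the cited series suggest, leaving them out makes the standard error somewhat too large (a stratified one would be about 2 to 6% smaller) and takes the one-sided error to about 1.9 to 2.3%. It forgoes roughly 1 to 2 points of power: about 1 point for one factor with the cited timing gaps, and nearer 2 only if both factors are strong.

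These sizes rest on assumed stratum rates and shares, good balance across arms, and calculations that ignore the interim look. If the factors turn out weakly prognostic, the gain shrinks towards nothing and little is lost by stratifying. That either factor is strongly prognostic in this trial's population is not established.

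**What to change.** Make the stratified risk difference the primary analysis. Use Mantel-Haenszel weights and a stratified variance over the four cells of planned type by timing, taken as recorded at randomisation. Keep the 0.10 margin, the 1.96 final boundary and the sample size. Use the same statistic at the futility look, with its stated boundary, so that both looks test the same quantity. Keep the crude Z as the sensitivity analysis.

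Because the trial is open-label, fix the estimator, the strata definition and the order of the two analyses in the plan before outcome data are compared by arm. This also settles which result prevails if the two fall on opposite sides of the boundary.

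The cost is small: two analyses already in the plan change places. One cell may be sparse, which Mantel-Haenszel weights handle. A switch to a 24-month cumulative incidence should not be folded into this change. It treats censoring and competing events differently and would need its own justification.
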